2.7.5 Sensitivity analyses

Not applicable.

2.7.6 Supplementary analyses

Other supplementary analyses comprise ORR per RECIST 1.1 as assessed by the Investigator (local assessment) along with 95% confidence intervals for cohort B and a summary of the reasons for ‘NE’ BOR, as well as DOR per RECIST 1.1 as assessed by the Investigator (local assessment), for cohort A and cohort B.

An assessment of the concordance between the BIRC assessment and the local assessment of the BOR for each participant will also be provided. The calculation will be based on the percent agreement (the proportion of response outcomes that agree across both independent reviewer and investigator assessments):

Percent Agreement = (Number of matched responders + Number of matched non-responders) / total number of subjects assessed.

2.8 Analyses supporting other secondary efficacy objectives

Other secondary efficacy objectives are:

- To assess the antitumor activity of JDQ443 single-agent as first-line treatment.
- To assess the antitumor activity of JDQ443 single-agent as first-line treatment for participants whose tumors harbor an STK11 mutation regardless of PD-L1 expression status (pooled from both cohorts).

The antitumor activity will be evaluated by the following endpoints: DCR, PFS, TTR, and OS. The analyses will be based on both central review and Investigator review per RECIST 1.1. The secondary efficacy endpoints will be assessed using the FAS.

2.8.1 Secondary efficacy endpoints

2.8.1.1 Disease control rate

Disease control rate is defined as the proportion of participants with a BOR of confirmed CR, PR, SD, or Non-CR/Non-PD as per Investigator or BIRC assessment based on RECIST 1.1. DCR will be analyzed using the same analytical conventions as for ORR.

2.8.1.2 Visualization of anti-tumor activity

Waterfall graphs will be used to depict the anti-tumor activity. One waterfall graph each will be constructed using the data from the Investigator assessments and the BIRC assessments.

These plots will display the best percentage change from baseline in the sum of diameters of all target lesions for each participant. Only participants with measurable disease at baseline will be included in the waterfall graphs.

Special consideration is needed for assessments where the target lesion response is CR, PR or SD, but the appearance of a new lesion or a worsening of non-target lesions results in an overall lesion response of PD. As a conservative approach, participants with such assessments will not be represented as bars in the waterfall graph but will be represented by a “zero” bar with a special symbol (e.g., *).

Assessments with NE target lesion response and assessments with NE overall response will be excluded from the waterfall graphs. Participants without any valid assessments will also be excluded from the waterfall graphs.

The total number of participants displayed in the graph will be shown and this number will be used as the denominator for calculating the percentages of participants with tumor shrinkage and tumor growth. A footnote will explain the reason for excluding some participants (due to absence of any valid assessment).

All possible assessment scenarios are described in [Table 2-6](#).

Table 2-7 Assessments considered for calculation of best percentage change for waterfall graphs

Case	Target response	Overall lesion response	Calculate % change from baseline in sum of diameters?
1	NE	Any	No, exclude assessment
2	Any	NE	No, exclude assessment
3	CR/PR/SD	PD	No, flag assessment with special symbol (*)
4	PD	PD	Yes
5	CR/PR/SD	CR/PR/SD	Yes

Based on the above considerations, the following algorithm will be used to construct the waterfall graph:

1. Select “valid” post-baseline assessments to be included, i.e., for each participant and each assessment repeat the following four steps.
 - a. Check the target lesion response and overall lesion response. If at least one of them is NE, then exclude the whole assessment. Otherwise, go to step 1.b.
 - b. Check the overall lesion response. If it is PD then go to step 1.c. Otherwise go to step 1.d.
 - c. Check target response. If it is PD then go to step 1.d. Otherwise flag the assessment with a special symbol (*).
 - d. Calculate the % change from baseline in target lesions.
2. For each participant, go through all valid assessments identified in step 1 and find the assessment with best % change from baseline in target lesions. The “best” means best for the participant, i.e., the largest shrinkage or if a participant only has assessments with tumor growth take the assessment where the growth is minimal.
3. Construct the waterfall graph displaying the best % change from baseline for each participant. Participants having only flagged assessment(s) (*) will be displayed separately.

The BOR will be shown above each of the displayed bars in the waterfall graph, if the number of participants displayed in the graph is small enough for the labels to be legible.

The order of the display from left to right will be as follows:

- Bars under the horizontal axis representing tumor shrinkage;
- Bars above the horizontal axis representing tumor growth;
- “Zero” bars with special symbol (*)�.

For each of the 3 categories above, n (%) (where % uses the total number of participants displayed in the waterfall graph) will be displayed. If there are any participants with zero change they will be shown as a separate category following participants with tumor shrinkage.

The swimmer plots will also be used to display the overall response of each participant over time, depicting the onset and duration of the different response categories.

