- If central radiology does not confirm progressive disease, the study site will be informed. As long as it is clinically acceptable, every effort should be made to continue the participant on study treatment until progressive disease is confirmed by BIRC or for at least one subsequent radiological timepoint.

Time points without locally determined progression

All imaging time points without locally determined progression will be read on an ongoing, non-expedited basis as detailed in the imaging manual to be provided by the designated imaging CRO and independent review charter. Results of these readings will not be communicated to the sites.

Treatment beyond disease progression

Following determination of disease progression, if the Investigator believes the participant treated with JDQ443 may derive benefit from continuing study treatment, the participant will be permitted to continue treatment beyond initial disease progression as per RECIST 1.1 by BIRC. Please see Section 6.1.4.1 for additional information.

Efficacy follow-up imaging assessments

For participants who discontinue treatment for reasons other than initial disease progression as per RECIST 1.1, tumor assessments must continue to be performed as outlined in Table 1-3 regardless if participants start on new antineoplastic therapy before documented disease progression. Please refer to Section 8.4 for additional information.

As per Section 4.5, during a Public Health emergency as declared by Local or Regional authorities i.e., pandemic, epidemic or natural disaster, that limits or prevents on-site study visits, the collection of images (e.g., change of imaging center or imaging frequency) may be modified by Novartis and will be communicated to the Investigator.

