2.6.1 Primary endpoint(s)

The primary clinical question of interest and the primary estimand are defined in [Section 1.2.1](#).

The primary endpoint is ORR, defined as the proportion of participants with a confirmed CR/PR as BOR. BOR is defined as the best response recorded from the start of the treatment until disease progression per RECIST 1.1 by BIRC. Complete and partial responses must be

confirmed by repeat assessments that should be performed not less than 4 weeks after the criteria for response were first met. Responses documented after the use of any new anti-neoplastic therapy will be considered as non-response (with the exception of protocol-allowed radiotherapy).

The BOR will be determined from response assessments undertaken while on treatment. In addition, only tumor assessments performed before the start of any further anti-neoplastic therapy (with the exception of protocol-allowed radiotherapy) will be considered in the assessment of BOR.

BOR for each participant is determined from the sequence of overall (lesion) responses according to the following rules:

- CR = at least two determinations of CR at least 4 weeks apart before progression;
- PR = at least two determinations of PR or better at least 4 weeks apart before progression (and not qualifying for a CR);
- SD = at least one SD assessment (or better) > 5 weeks after start of treatment (and not qualifying for CR or PR);
- Non-CR/non-PD* = at least one Non-CR/non-PD assessment > 5 weeks after start of treatment (and not qualifying for CR);
- PD = progression ≤ 13 weeks after start of treatment (and not qualifying for CR, PR or SD);
- NE = all other cases (i.e., not qualifying for confirmed CR or PR and without SD after more than 5 weeks or early progression within the first 13 weeks).

* For participants with only non-measurable disease present at baseline. A non-CR/non-PD response is considered equivalent to an SD response for the ORR determination and participants will be considered “non-responders”.

Participants with ‘NE’ BOR will be summarized by reason for having NE status. The following reasons will be used:

- No valid post-baseline assessment
- All post-baseline assessments have overall lesion response NE
- New anti-neoplastic therapy started before first post-baseline assessment
- SD too early (≤ 5 weeks after start of treatment)
- PD too late (> 13 weeks after start of treatment)

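### The SAP's waterfall rules give two different zero-bar definitions and no cut at new anticancer therapy, so the percentages with tumor shrinkage, growth and zero bars are not uniquely defined and shrinkage can be inflated

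*SAP*

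**What the plan says.** SAP 2.8.1.2 plans one waterfall graph from BIRC data and one from investigator data. It requires n (%) for shrinkage, growth and zero bars. The number of participants displayed is shown, and "this number will be used as the denominator for calculating the percentages of participants with tumor shrinkage and tumor growth".

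- **Which scans count (step 1).** The target and overall lesion responses are checked: "If at least one of them is NE, then exclude the whole assessment". If the overall response is PD, the target response is examined. Where that is also PD the change is measured. "Otherwise flag the assessment with a special symbol". No other filter is stated.
- **Which value is plotted (step 2).** The programmer is to "go through all valid assessments identified in step 1 and find the assessment with best % change from baseline in target lesions".
- **Zero bars, narrative.** For scans with a target response of CR, PR or SD but overall PD, "participants with such assessments will not be represented as bars in the waterfall graph but will be represented by a" zero bar with a symbol.
- **Zero bars, algorithm (step 3).** "Participants having only flagged assessment(s) (*) will be displayed separately".

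Two passages elsewhere bear on this. For BOR, SAP 2.6.1 uses "only tumor assessments performed before the start of any further anti-neoplastic therapy", with protocol-allowed radiotherapy exempt. Protocol 8.4.1 requires imaging of participants who stop treatment without progression to go on "regardless if participants start on new antineoplastic therapy before documented disease progression".

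**The concern.** The narrative zero-bar rule works on the participant: one flagged scan is enough. Step 3 requires that every usable scan be flagged. The two cannot both be programmed, and they disagree about participants a waterfall is meant to show, namely those whose target lesions shrank before a new or non-target lesion ended the response.

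Separately, step 1 decides usability by response category alone, and SAP 2.1.1 takes all data up to the cut-off. A scan made after the next anticancer therapy has started therefore competes for best change on equal terms with scans on JDQ443. The primary estimand is justified by avoiding that confounding, and BOR (SAP 2.6.1, 2.6.3), DOR (2.7.3) and PFS (2.8.1.4) each have a rule for it. The waterfall has none. Because BOR is to be printed above the bars where legible, a bar and its label could rest on different scans.

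At stake are the counts and percentages attached to a display of antitumor activity in an open-label, single-arm trial, where a rule chosen after the data are seen is hard to defend.

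**Working it through.** Neither document states a shrinkage percentage, so there is no figure to reproduce. The check applies steps 1 to 3 to constructed participants, each with a baseline sum of diameters of 100 mm, and then computes the effect of one reclassified participant. Change = 100 × (sum − baseline) / baseline.

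| Participant | Post-baseline scans (sum; target / overall) | Steps 1–3 as written | Alternative |
|---|---|---|---|
| A | 60 PR/PR; 60 PR/PR; 60 PR/PD (new lesion) | 100 × (60 − 100)/100 = −40% | Narrative rule: zero bar |
| B | 105 SD/SD; 110 SD/SD; new therapy; 75 SD/SD | 100 × (75 − 100)/100 = −25% | Cut at new therapy: 100 × (105 − 100)/100 = +5% |
| C | 60 PR/PR; 75 PD/PD; 80 PD/PD | −40% | Cut at first PD: still −40% |

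A shows the conflict between the two zero-bar rules. B shows growth on JDQ443 turning into shrinkage because of a later therapy. C shows that scans with both responses PD do no harm: target PD is defined against the smallest earlier sum (Protocol 10.8.2.4.2), so such a scan cannot beat a usable nadir scan. Scans with overall PD and a non-PD target are flagged and not measured. A scan after progression can therefore deepen a usable earlier best only if its overall response is again recorded as something other than PD.

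**Who is affected by the zero-bar conflict**

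- Only flagged scans: zero bar under both rules, so no change.
- Measured growth plus a flagged scan: growth under step 3, zero under the narrative. The shrinkage percentage does not change.
- Measured shrinkage plus a flagged scan: shrinkage under step 3, zero under the narrative. The shrinkage percentage changes.

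**Who is affected by the missing therapy cut.** Participants who start new therapy before documented progression, keep being scanned, and have their best change after the switch. Protocol 8.4.1 leaves routes to this. One is stopping for another reason, such as toxicity, and then starting new therapy. Another is locally called progression that BIRC does not confirm, with therapy changed for medical need.

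**Size.** If k participants change shrinkage status among N displayed, the percentage moves by 100 × k / N. The values of k are assumptions. N is set to the planned cohort sizes (SAP section 3).

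| k | N = 90 (cohort A) | N = 30 (cohort B) |
|---|---|---|
| 1 | 1.1 points | 3.3 points |
| 3 | 3.3 points | 10.0 points |
| 5 | 5.6 points | 16.7 points |

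The number displayed may fall below the cohort size, because participants without measurable disease or without any valid assessment are left out. Each participant would then weigh slightly more.

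**The case against.** The strongest reply is that the operative rule can be identified. SAP 2.8.1.2 introduces the numbered steps as the way the graph will be built, Table 2-7 flags the assessment rather than the participant, and step 3 fits both. On that view one introductory sentence is loose, and a programmer following the steps would keep responders as shrinkage bars. Much of this stands, and it is why the fix adopts step 3. But the SAP does not say which text prevails, and the narrative presents its rule as the deliberately cautious choice, so the intended rule is not shown. The reply also does nothing for the second gap, which comes from following the steps faithfully.

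It is also fair that the plot is descriptive. It tests no hypothesis and enters no success or futility criterion. That stands and limits the importance of the point.

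A reader might infer more than the documents support:

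- **That scans after progression generally inflate the plot.** They do not, for the reasons shown by participant C. Protocol 6.1.4.1 also allows treatment beyond progression only if no new antineoplastic therapy has begun, so on-treatment scans in that group reflect JDQ443.
- **That everyone who progresses through a new or non-target lesion is affected.** Those with only flagged scans are plotted the same way under both rules.
- **That a deep bar labelled SD signals an error.** It can be legitimate: an unconfirmed PR can give a BOR of SD and still show shrinkage of 30% or more.

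**Conclusion.** The point holds as a gap in specification with a possible upward bias. The zero-bar rules conflict for participants who have both a flagged and a measured assessment. The shrinkage percentage changes for those whose measured best change was shrinkage, and step 3 gives the higher figure. The missing cut at new anti-neoplastic therapy lets next-line shrinkage count as a JDQ443 effect. The lack of a stop at first PD matters only where a later scan is again rated non-PD overall.

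The effect is about 1.1 points per participant with 90 displayed and 3.3 with 30, assuming all planned participants appear in the plot. How many would be reclassified cannot be derived from the documents. It would go too far to say that the shrinkage percentage is wrong, because none is reported; it is not uniquely defined and is open to inflation. ORR, DOR and PFS have their own new-therapy rules and are untouched.

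**What to change.** Make two changes in SAP 2.8.1.2.

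1. Replace the narrative zero-bar sentence with: *Participants whose only valid assessments are flagged will be represented by a zero bar.* This matches step 3.
2. In step 1, restrict assessments to post-baseline scans up to and including the first overall PD and before any new anti-neoplastic therapy other than protocol-allowed radiotherapy.

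Write the second restriction out in full rather than refer to the scans used for BOR. SAP 2.6.1 describes BOR as based on assessments made on treatment, while 2.6.3 includes those made after discontinuation, so a cross-reference would import that difference.

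The cost is two sentences in the SAP and one filter in the program. No new data are needed.

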2.8.1.3 Time to response

Time to response is defined as the time from the date of first dose of study treatment to the first documented response (CR or PR, which must be confirmed subsequently). TTR will be evaluated based on Investigator or BIRC assessment according to RECIST 1.1.

All participants in the FAS will be included in TTR calculations. Participants who did not achieve a confirmed CR or PR will be censored at the last adequate tumor assessment date when they did not have a PFS event (i.e., radiological disease progression or death due to any cause) or at maximum follow-up (i.e., $LPLV - FPFV + 1$ used for the analysis) when participants had a PFS event.

TTR will be summarized by descriptive statistics by cohort. The TTR distribution will be estimated using the Kaplan-Meier method, and the Kaplan-Meier curves, medians and 95% confidence intervals of the medians will be presented for each cohort. TTR data will also be listed.

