9.4.1.2 Other secondary efficacy endpoints

DCR is defined as the proportion of participants with a BOR of confirmed CR, PR and stable disease (SD) according to RECIST 1.1 (see Appendix 8 Section 10.8). DCR will be assessed by BIRC as well as by local review. DCR and the corresponding 95% confidence intervals based on the exact binomial distribution (Clopper and Pearson 1934) will be presented.

PFS is defined as the time from the date of first dose of study treatment to the date of the first documented progression or death due to any cause. PFS will be assessed by BIRC as well as by local review according to RECIST 1.1 (see Section 10.8 for further details). PFS will be censored if no PFS event is observed before the first to occur between: (i) the analysis cut-off date, and (ii) the date when a new anti-neoplastic therapy is started. The censoring date will be the date of the last adequate tumor assessment prior to cut-off/start of new anti-neoplastic therapy. The PFS distribution will be estimated using the Kaplan-Meier method, and the Kaplan-Meier curves, medians and 95% confidence intervals of the medians will be presented for each cohort.

Time to response (TTR) is defined as the time from the date of first dose of study treatment to the first documented response of either CR or PR, which must be subsequently confirmed (although date of initial response is used, not date of confirmation). CR and PR are based on tumor response data by BIRC as well as per local review and according to RECIST 1.1 (see Section 10.8 for details). All participants in the FAS will be included in TTR calculations. Participants without a confirmed CR or PR will be censored at the study-maximum follow-up time (i.e., LPLV-FPFV) for participants with a PFS event (i.e., disease progression or death due to any cause), or at the date of the last adequate tumor assessment for participants without a PFS event. TTR will be listed and summarized by cohort. The TTR distribution will be estimated using the Kaplan-Meier method, and the Kaplan-Meier curves, medians and 95% confidence intervals of the medians will be presented for each cohort.

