10.8.3.2.7 Time to response

Time to overall response (CR or PR) is the time between date of randomization/start of treatment until first documented response (CR or PR). The response may need to be confirmed depending on the type of study and its importance. Where the response needs to be confirmed then time to response is the time to the first CR or PR observed.

Although an analysis on the full population is preferred a descriptive analysis may be performed on the "responders" subset only, in which case the results should be interpreted with caution and in the context of the overall response rates, since the same kind of selection bias may be introduced as described for duration of response in Section 10.8.3.2.6. It is recommended that an analysis of all participants (both responders and non-responders) be performed whether or not a "responders only" descriptive analysis is presented. Where an inferential statistical comparison is required, then all participants should definitely be included in the analysis to ensure the statistical test is valid. For analysis including all participants, participants who did not achieve a response (which may have to be a confirmed response) will be censored using one of the following options:

- at maximum follow-up (i.e. FPFV to LPLV used for the analysis) for participants who had a PFS event (i.e. progressed or died due to any cause). In this case the PFS event is the worst possible outcome as it means the patient cannot subsequently respond. Since the statistical analysis usually makes use of the ranking of times to response it is sufficient to assign the worst possible censoring time which could be observed in the study which is equal to the maximum follow-up time (i.e. time from FPFV to LPLV)
- at last adequate tumor assessment date otherwise. In this case participants have not yet progressed so they theoretically still have a chance of responding

Time to overall complete response (CR) is the time between dates of randomization/start of treatment until first documented CR. Similar analysis considerations including (if appropriate) censoring rules apply for this endpoint described for the time to overall response endpoint.

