2.6.3 Handling of intercurrent events

The primary analysis will account for different intercurrent events as follows:

1. Discontinuation of study treatment: Tumor assessment data collected after discontinuation of study treatment for any reason will be included to derive BOR (treatment policy strategy).
2. Start of a new anti-neoplastic therapy: If any new anti-neoplastic therapy is initiated, responses documented after the use of new anti-neoplastic therapy will be considered as non-response (composite strategy). Protocol-allowed radiotherapy is exempted.
3. Any public health emergency as declared by local or regional authorities, i.e., pandemic, epidemic or natural disaster: Tumor assessment data collected irrespective of such unforeseen events will be considered for the BOR (treatment policy strategy).

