2.8.1.4 Progression-free survival

Progression-free survival is defined as the time from the date of first dose of study treatment to the date of the first documented progression or death due to any cause. PFS will be evaluated based on Investigator or BIRC assessment according to RECIST 1.1.

PFS will be censored if no PFS event (radiological progression or death) is observed prior to the first to occur between: (i) the analysis cut-off date, and (ii) the date when a new anti-neoplastic therapy (with the exception of protocol-allowed radiotherapy) is started. The censoring date will be the date of the last adequate tumor assessment prior to cut-off/start of new anti-neoplastic therapy.

Clinical deterioration will not be considered as documented disease progression. A PFS event date will be included in the analysis if it occurs after one missing tumor assessment. If the PFS event is observed after two or more consecutive missing tumor assessments, PFS will be censored at the last adequate tumor assessment prior to the first missing assessment.

The date of last adequate tumor assessment is the date of the last tumor assessment with overall lesion response of CR, PR, SD, or non-CR/non-PD before an event or a censoring reason occurred. In this case the last tumor evaluation date at that assessment will be used. Participants without a post-baseline tumor assessment will be censored at the date of first dose of study treatment.

A missing adequate tumor assessment is defined as a tumor assessment (TA) not performed or a tumor assessment with overall lesion response of “not evaluable (NE)”. The rule to determine the number of missing TAs is based on the time interval between the date of last adequate tumor assessment and the date of an event. Details are described in [Section 4.5](#).

[Table 2-5](#) shows the censoring and event date options and the outcomes for PFS. Details about censoring rules for PFS follow the RECIST 1.1 guidelines ([\[Study Protocol Section 10.8\]](#)) and are provided in [Section 4.5](#).

The distribution of PFS will be estimated using the Kaplan-Meier method, and the Kaplan-Meier curve, median, and 95% CI of the median will be presented by cohort.

A subgroup analysis of PFS will be prepared for cohort A for the subgroups 4a to 4h.

Censoring pattern for PFS

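### Time to response censors non-responders who start new anticancer therapy as if they could still respond, so the Kaplan-Meier response curve can exceed the ORR

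*SAP*

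**What the plan says.** SAP 2.8.1.3 analyses TTR in everyone: "All participants in the FAS will be included in TTR calculations". It also specifies the estimator: "The TTR distribution will be estimated using the Kaplan-Meier method", with a median and 95% confidence interval per cohort. Participants without a confirmed CR or PR fall under one of two censoring rules:

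- They are censored at maximum follow-up "when participants had a PFS event". This keeps them in the risk set throughout.
- Otherwise they "will be censored at the last adequate tumor assessment date when they did not have a PFS event".

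Protocol 9.4.1.2 has the same split, with censoring "at the date of the last adequate tumor assessment for participants without a PFS event". Neither section mentions new anticancer therapy.

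Protocol 10.8.3.2.7 explains the split. After a PFS event the patient can no longer respond, so the worst possible censoring time is assigned. Of the others it says: "In this case participants have not yet progressed so they theoretically still have a chance of responding".

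Two further rules decide where a switcher lands. In SAP 2.8.1.4, PFS is censored if no event precedes the earlier of the cut-off and "ii) the date when a new anti-neoplastic therapy (with the exception of protocol-allowed radiotherapy) is started"; SAP Table 2-6 likewise lists new therapy before progression as censored. For ORR, SAP 2.6.3 states that "responses documented after the use of new anti-neoplastic therapy will be considered as non-response (composite strategy", and SAP 2.6.1 uses only assessments made before new therapy to derive best overall response.

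**The concern.** Take a non-responder who starts new therapy before any PFS event. PFS is censored, so the second TTR rule applies and the participant leaves the risk set at the last adequate assessment. The stated reason for that rule is that a response is still possible. For this participant it is not, because nothing seen after the switch can count. By the protocol's own reasoning the participant belongs with those held to maximum follow-up.

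Removing people who cannot respond shrinks the denominator for later responses and raises the Kaplan-Meier curve. The report could then show a response probability by TTR above the ORR in the same participants. If the curve is pushed past 50%, it could also show a finite median TTR although fewer than half responded.

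The plan foresees such participants. Protocol 8.4.1 allows an immediate change of therapy for medical need when central review does not confirm local progression, and it continues imaging in those who start new therapy before documented progression.

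**Working it through.** The documents state no TTR figure, switch rate or response timing, so there is no plan figure to reproduce. The check is whether, and by how much, the curve can leave the ORR.

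**Inputs.** Cohort A size of 90 and scans every 6 weeks to week 54 come from SAP sections 3 and 4.5. Assumed: first documentation of confirmed responses in 27, 9 and 3 participants at weeks 6, 12 and 18 (39/90 = 43.3%); c switchers; all other non-responders censored at maximum follow-up; no other early censoring.

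**Formula.** Someone censored at week 6 is still at risk for the week-6 responses and is removed afterwards. The plateau of the response curve is then

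1 − (63/90) × (54 − c)/(63 − c) × (51 − c)/(54 − c) = 1 − 0.7 × (51 − c)/(63 − c).

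| Switchers | Censored at | Calculation | Plateau |
|---|---|---|---|
| 0 | – | 1 − 0.7 × 51/63 | 43.3% |
| 3 | week 6 | 1 − 0.7 × 48/60 | 44.0% |
| 5 | week 6 | 1 − 0.7 × 46/58 | 44.5% |
| 9 | week 6 | 1 − 0.7 × 42/54 | 45.6% |
| 18 | week 6 | 1 − 0.7 × 33/45 | 48.7% |
| 9 | week 12 | 1 − 0.7 × 54/63 × 42/45 | 44.0% |
| 9 | week 18 | 1 − 0.7 × 54/63 × 51/54 | 43.3% |

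**Direction.** The ratio (51 − c)/(63 − c) falls as c rises, so this censoring can only raise the curve. In general, taking a non-responder out of the risk set increases the estimated hazard at every later response time. The last row shows the condition: if no response is first documented after the switchers' censoring date, there is no excess.

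**Median.** None of these curves reaches 50%, so none gives a median. For a case that does, take 41/90 = 45.6%, the smallest count whose exact lower 95% limit reaches the 35% required in SAP 2.6.2 (35.02%; 40/90 gives 33.96%). Assume responses 29/8/4 at weeks 6/12/18.

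- Nine switchers with no adequate post-baseline assessment, censored at first dose: 41/81 = 50.6%.
- Eighteen switchers censored at week 6: 1 − (61/90) × (31/43) = 51.1%.

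Both curves would yield a median TTR although 45.6% responded.

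**Under the proposed rule.** With switchers held to maximum follow-up, the plateau returns to 43.3% and 45.6% respectively, given no other early censoring.

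**The case against.** **Scale.** Nine or 18 switchers would be 18% or 35% of the 51 non-responders, all leaving after the first scan without central progression. The protocol works against that. Treatment should continue while central review is awaited, review is expedited to 5 business days, and if progression is not confirmed, treatment should go on to at least one further assessment unless there is medical need. This stands. Small counts are the more plausible range, and at 3 to 5 switchers the excess is about one point.

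**A literal reading of the text.** SAP 2.8.1.3 describes a PFS event as radiological progression or death. Imaging and survival follow-up continue after new therapy, so a switcher who later progresses or dies might already go to maximum follow-up. The PFS derivation in SAP 2.8.1.4 does not count that event. The text is ambiguous here, but switchers with no later event are affected on either reading.

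**Borrowed strategy.** The composite handling of new therapy belongs to the ORR estimands, and no estimand is defined for TTR. That is true, and SAP 2.8.1.3 does not expressly bar later responses. If they were allowed, however, TTR would count responders that the ORR rejects, and the two endpoints would still disagree.

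**Low stakes.** TTR is untested and reported beside the ORR. TTR data, post-treatment therapies and PFS censoring reasons are all listed or summarized. This limits the harm but does not justify the rule.

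A reader might also infer that the curve always exceeds the ORR, that the median is generally shortened, or that a cohort with more switching is favoured. The documents support none of these. The excess is conditional, a median arises only if the curve reaches 50%, and the cohorts are expressly non-comparative.

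**Conclusion.** The inconsistency is real. The TTR censoring rule rests on a continuing chance of response that SAP 2.6.1 and 2.6.3 remove once new therapy starts. From this cause the curve can exceed the ORR and cannot fall below it. A strict excess needs at least one confirmed response first documented after a switcher's censoring date.

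On the assumed response pattern the excess runs from about one point with 3 to 5 early switchers to a little over five points with 18, and it vanishes if switching comes after the last response. A misleading finite median is possible only with an ORR not far under 50% and enough early switching. All these sizes depend on assumed timing and switch counts.

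A reader might infer that the primary result is biased; it is not. The ORR, its exact interval and its test do not use the TTR rule. This is a correction to a descriptive secondary endpoint, worth making before database lock.

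**What to change.** Replace the censoring sentence in SAP 2.8.1.3 with: *Participants without a confirmed CR/PR who had a PFS event, or who started new anti-neoplastic therapy (except protocol-allowed radiotherapy), are censored at maximum follow-up, regardless of any later progression or death; all others are censored at the last adequate tumor assessment.* The words on later progression or death also settle the ambiguity about what counts as a PFS event after a switch.

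The cost is one SAP clause and a small programming change. The therapy start date is already needed for ORR, DOR and PFS. Protocol 10.8.4.1 allows such details to be settled in the analysis plan, so the SAP change need not wait for a protocol amendment; protocol 9.4.1.2 can be aligned at the next one.

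The clause removes the new-therapy component only. Participants lost to follow-up, withdrawn or without an adequate post-baseline assessment are also censored early for TTR while counting as non-responders for ORR, so the two figures may still differ. A footnote to the TTR output should say so.
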